**Version**

1.3

**Version date**

06.07.2025

**Overview**

Date	Version	Status	Adjustments
23.04.2025	1.0	Draft	
23.05.2025	1.1	Draft	Inclusion of funding source
02.06.2025	1.2	Draft	Adaption of number of participants
06.07.2025	1.3	Draft	Addition of references to scientific background
02.09.2025	1.4	Draft	Addition of recommendations from the Ethics Committee

## **ZUSAMMENFASSUNG/PROJECT SUMMARY**

With increasing survival rates in pediatric oncology, reports of long-term side effects persisting decades after treatment are also rising. Clinically evident nephropathies occur in about 5.5% of survivors more than five years after therapy. Chemotherapeutic agents such as ifosfamide, cisplatin, and carboplatin, as well as kidney-directed treatments like radiation, surgery, or stem cell transplantation, increase this risk. Acute kidney injury has also been described in association with cyclophosphamide and high-dose methotrexate, which are used in the treatment of acute lymphoblastic leukemia (ALL). Studies show a high prevalence of albuminuria (around 14.5% of childhood cancer survivors), an early marker of kidney damage, while standard parameters like creatinine often become abnormal only at later stages.

Leukemia survivors suffer from vascular late effects caused by persistent endothelial damage triggered by cancer therapies such as anthracyclines, cyclophosphamide, and asparaginase, which increase inflammation and thrombosis risk. These vascular changes may also contribute to kidney injury.

ULM is a high-resolution ultrasound technique that uses microbubbles to visualize the microvasculature and resolve dynamic blood flow changes with a resolution beyond the diffraction limit. ULM is independent of kidney or liver function, has been applied in various organs, and was recently used for the first time to visualize glomeruli—the smallest functional units of the kidney—in humans. This method enables early detection of glomerular injury as a consequence of vascular damage, even before albuminuria appears, potentially allowing earlier adaptation of follow-up and initiation of treatment.

This pilot project focuses on survivors of ALL, as they are the largest and best studied pediatric cancer patient group also regarding late effects and, therefore, a sufficient number of individuals can be expected for his monocentric approach. Vascular functional impairment of the kidney could be detected at an early stage and the follow-up structures and measures such as the early use of nephroprotective drugs could be adapted.

## **Funding**

Internal funds of the Children's Hospital Erlangen until application for external funds

## **SCIENTIFIC BACKGROUND**

In parallel to increasing survival rates in pediatric oncology, a growing number of studies describe an increase in long-term side effects even decades after cancer treatment in childhood and adolescence [1].

### **Long-Term Nephrotoxicity in Childhood and Adolescent Cancer Survivors**

Nephropathies occur in 5.5% of survivors more than 5 years after the end of therapy [2]. Chemotherapeutic agents with well documented early nephrotoxicity are ifosfamide, cisplatin, and carboplatin. A limited number of studies only evaluated long-term risk and risk factors for renal toxicity, and these studies were performed in selected groups of survivors with a maximum of 10 years' follow-up [3]. Other risk factors for nephrotoxicity include kidney radiotherapy (including whole body radiotherapy in the setting of stem cell transplantation), kidney surgery, or stem cell transplantation [4]. Acute nephrotoxicity has also been described with cyclophosphamide and high-dose methotrexate [3, 5, 6], both drugs used in the treatment of acute lymphoblastic leukaemia (ALL). There is a general lack of data or studies in other groups of cancer survivors.

Few studies describe a high prevalence and risk of reduced kidney function in the form of low GFR, albuminuria, or increased blood pressure in long-term survivors of childhood and adolescent cancer. For example, Knijnenburg et al. found albuminuria in 14.5% of 1442 childhood and adolescent cancer survivors analysed (0.7% in the normal population comparison group) [3]. Albuminuria is generally considered to be an early and sensitive marker in the presence of an often normal GFR [7]. Blood markers, such as creatinine or eGFR, are less sensitive because they are generally only detectable at late stages of kidney damage. However, given the lack of more sensitive alternatives as early indicators of chronic renal toxicity, markers such as creatinine or GFR are often used to monitor kidney function in regular (long-term) follow-up after childhood and adolescent cancer. Against this background, the establishment of sensitive methods facilitating and early detection of kidney damage appears to be of great value.

### **Endothelial Injury and Long-Term Vascular Toxicity in Leukemia Survivors**

Cancer therapies can lead to a broad spectrum of cardiovascular complications. Among these, cardiotoxicities remain of prime concern, but vascular toxicities have emerged as the second most common group [8]. Studies have shown that particularly leukemia survivors suffer from vascular late effects [9]. Growing evidence suggests that chemotherapeutics affect endothelial function, reduce nitric oxide (NO) bioavailability, and lead to endothelial cell activation.

Resulting endothelial dysfunction is associated with tissue ischemia, hampered vascular barrier function, atherosclerosis, and altered hemodynamics [10]. Cancer therapies can induce and exacerbate endothelial injury through direct cytotoxic and cytostatic effects on endothelial cells, while also impairing repair mechanisms by reducing endothelial cell proliferation and the number of endothelial progenitor cells. Notably, endothelial dysfunction may persist long after treatment, as studies in long-term cancer survivors have shown signs of ongoing endothelial activation and elevated levels of circulating endothelial cells even decades after therapy.[8] Endothelial injury disrupts vascular homeostasis, leading to inflammation, impaired repair mechanisms, and a prothrombotic state, thereby contributing directly to the development of vascular damage.

Different drugs are used in the therapy of ALL that cause vascular damage. Anthracyclines cause endothelial damage [11], Cyclophosphamide metabolites are believed to cause oxidative stress and direct endothelial capillary damage [12], Asparaginase is an essential drug for the treatment of ALL, may increase the risk of thrombosis or bleeding, the incidence of symptomatic asparaginase-associated thrombosis ranges from 2–7% in clinical trials [13].

**As vascular late effects such as coronary artery disease caused by endothelial impairment are common late effects in childhood cancer survivors, it is reasonable that nephropathy in childhood cancer survivors may at least in part also be caused by vascular or endothelial effects in addition to a tubular damage [9, 14].**

#### **Visualizing Glomerular Injury: A New Frontier with Ultrasound Localization Microscopy**

Ultrasound Localization Microscopy (ULM) is an **advanced and highly sensitive ultrasound imaging technique** that allows visualisation of the microvasculature and quantification of dynamic blood flow changes within the vascular architecture with unprecedented resolution. Tiny air bubbles (microbubbles) are administered intravenously as contrast agents, which can then be localised and tracked within each image of the ultrasound acquisition [15]. Accumulation of all these tracks on a 2D grid produces a microvascular map of the organ with a resolution beyond the diffraction limit of ultrasound waves. Unlike other types of contrast agents, the microbubbles are subsequently metabolised independently of kidney and liver function and will simply be washed out by respiration [16]. ULM has been used in several human organs [17-19]. Two studies have already been performed at the Department of Pediatrics and Adolescent Medicine (University Hospital Erlangen) using ULM to visualise the microvascular architecture in the neonatal brain and to quantify dynamic perfusion changes [18, 20]. Moreover, a study with ULM in kidney transplants has been successfully conducted, proving the feasibility of the method in patients with renal impairment. More recently, the glomerulus, the smallest functional unit of the kidney, has been visualised in the human body

with high resolution [21]. Glomerular injury is closely linked to vascular damage in the kidneys, as endothelial dysfunction and microvascular injury impair glomerular filtration and contribute to progressive renal dysfunction.

The aim of this study is to facilitate the early visualization of glomerular damage representing a vascular component of chemotherapy induced nephrotoxicity by ULM. This approach could contribute to the timely detection of functional kidney impairment - even earlier than potential albuminuria - and thus help to adapt follow-up structures and measures or even revise treatment protocols. In the frame of this pilot study, we focus on individuals with a history of ALL, as they represent by far the largest and most extensively studied subgroup of patients in pediatric oncology. Therefore, we expect a sufficient number of patients in this monocentric approach.

## **OBJECTIVES**

### **Hypotheses**

- ULM can be used to visualise and quantify the microvascular perfusion dynamics in the kidney and differs depending on the organ function
- Treatment of acute lymphoblastic leukaemia leads to (often subclinical) acute and chronic impairment of renal function also through vascular injury which can be visualized by ULM.

### **Primary objectives**

- ULM: Visualisation of microvascular architecture and Quantification of microvascular perfusion dynamics in the kidney before, during, and after treatment of acute lymphoblastic leukaemia

### **Secondary objectives**

- ULM: Correlation of the vascular architecture of the kidney **visualised** by ULM before, during and after treatment of acute lymphoblastic leukaemia (e.g. number of segmented glomeruli) with laboratory chemical parameters (including renal function parameters, inflammation parameters, immunological parameters)
- ULM: Correlation of vascular architecture of the kidney **visualised** using ULM before, during and after treatment of acute lymphoblastic leukaemia (e.g. number of segmented glomeruli) with sonographic parameters (e.g. resistance index (RI), flow velocity)
- ULM: Correlation of parameters of **quantified** microvascular perfusion dynamics of the kidney before, during and after treatment of acute lymphoblastic leukaemia with

laboratory chemical parameters (e.g. renal function parameters, inflammation parameters)

- ULM: Correlation of parameters of the **quantified** microvascular perfusion dynamics of the kidney before, during and after treatment of acute lymphoblastic leukaemia with sonographic parameters (including resistance index (RI), flow velocity)

### **Study type**

Prospective, monocentric, diagnostic study

### **OUTCOME MEASURES**

All ULM measurements will be performed on the kidney, which is better visualized in sonography.

#### *Primary outcome measures collected by ULM*

ULM: Visualisation of the microvascular architecture of the kidney

- ULM: Quantification of perfusion dynamics in one kidney (including measurement of peak enhancement (PE), wash-in area under the curve (WIAUC), wash-in perfusion index (WiPI), wash-in rate (WIR), wash-out area under the curve (WoAUC), wash-in and wash-out area under the curve (WiWoAUC), wash-out rate (WoR), time to peak (TTP), rise time (RT), mean transit time (local) (mTTI) and fall time (FT)).

#### *Secondary targets determined by laboratory chemistry*

- Laboratory chemistry parameters (including BB, Diff, Glucose, Na, K, Cl, Ca, LDH, Crea, Cystatin C, Uric Acid, CRP, Albumin, Ferritin, Total Protein)
- Urinalysis: including urinary status, proteinuria/haematuria

#### *Secondary outcome measures to be determined sonographically*

- Sonographic parameters (including resistance index (RI), Doppler signal, flow velocity, and others)

#### *Routine clinical practice measures (not related to the study)*

- Collection of clinical data from medical records (these outcome measures are available from medical records or will also be collected at initial presentation)

## **STUDY DESIGN**

### **Monocentric / multicentric**

This is a monocentric study

### **Study arms: interventional/control**

Patients fulfilling the inclusion criteria will receive ULM of one kidney. Patients with recently diagnosed ALL will receive ULM at two timepoints whereas participants in the oncological follow up after treatment for ALL will be examined at a single visit.

### **Randomization**

[figure not shown]
Randomization is not planned

### **Blinding**

Blinding to the study is not possible. Blinding of patients/subjects is not necessary

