### **Pseudonymisation**

Prior to a scientific analysis of the data from this study, all information is pseudonymised in accordance with the guidelines of the Federal Data Protection Act.

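### The protocol rules out blinding for the whole study, although ULM images could be processed and read on coded files with cohort, visit and laboratory values hidden

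*Protocol*

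**What the plan says.** The Blinding section consists of two statements: "Blinding to the study is not possible" and "Blinding of patients/subjects is not necessary". Patients are the only role treated separately. The scanning operator, the person who processes the images, the reader and the analyst are not mentioned, and no other section provides for masked reading.

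The two primary outcomes are both ULM products: "ULM: Visualisation of the microvascular architecture of the kidney", for which no reading rule is given, and "ULM: Quantification of perfusion dynamics in one kidney", an open list that names 11 parameters. The Secondary objectives add a segmentation product as an example of vascular architecture ("e.g. number of segmented glomeruli").

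Three other places bear on what is feasible:
- The Scientific Background describes microbubbles "which can then be localised and tracked within each image of the ultrasound acquisition", with the tracks then accumulated into a map.
- The Pseudonymisation section states: "Prior to a scientific analysis of the data from this study, all information is pseudonymised".
- The opening of Outcome Measures states: "All ULM measurements will be performed on the kidney, which is better visualized in sonography".

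**The concern.** The blinding statement is a design position, not a detail left for a later document. An analysis plan or imaging manual that introduced masked reading would sit awkwardly beside it, and an imaging team that takes it at face value has no reason to mask anyone.

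The design offers little other protection against reader expectation. There is no randomisation and no untreated comparison group. The second hypothesis is directional: it expects treatment to impair the kidney in a way that ULM can show. A reader who knows that an image comes from the second visit, or from the follow-up cohort, knows which result is hoped for. A reader who also knows creatinine, cystatin C or proteinuria could, without intending it, pull the ULM reading towards those values and so strengthen the correlations that make up all four secondary objectives.

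The section on the number of patients gives the pilot the task of estimating effect sizes for larger studies. A reading bias would be carried into the planning of those studies.

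**Working it through.** **Step 1: the plan's own figure.** The blinding statement has no number. The only figure that can be checked is the workload: 10 × 2 + 20 × 1 = 40 examinations in 10 + 20 = 30 patients. This agrees with the protocol. No power calculation can be reproduced, because the protocol makes none.

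**Step 2: which roles can be masked.** Setting the sections side by side:

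| Stage | What the protocol says | Can cohort and visit be hidden? |
|---|---|---|
| Choice of kidney and scanning | The better visualised kidney is scanned, during a chemotherapy or aftercare visit | Not readily: the operator sees the patient |
| Building the map | Bubbles are localised and tracked in acquired images, then accumulated | Yes: this works on acquired data |
| Segmentation (secondary objectives) | Number of segmented glomeruli, given as an example | Yes, on coded files |
| Perfusion quantification (primary) | 11 named parameters in one kidney | Yes, on coded files, if done after the scan; the protocol does not give the procedure |
| Analysis | Data are pseudonymised beforehand | Only if the code conceals cohort and visit, which is not stated |

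The blanket statement is therefore right for the first row and too wide for the others. The pseudonymisation step shows that a code will exist. It is written as data protection, and nothing says that the code hides cohort or visit from whoever reads the images.

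**Step 3: what a reading shift would do (illustration only).** The document gives no figure for reader bias, so a shift of b SD is assumed, with no true difference. Two-sided tests at 0.05, 20,000 simulated data sets per row:

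| Assumed shift b | Mann-Whitney, 10 vs 20 (b in between-patient SDs) | Paired t-test, n = 10 (b in SDs of the within-patient difference) |
|---|---|---|
| 0 | 4.4% | 5.1% |
| 0.25 | 8.3% | 11.0% |
| 0.5 | 21.0% | 30.1% |
| 1.0 | 66.0% | 79.8% |

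The protocol names the Mann-Whitney test and ANOVA. It names no paired test, so the right-hand column is a stand-in for the before/after contrast.

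The two columns use different units. With equal variances, SD of the difference = SD × √(2(1 − ρ)), where ρ is the correlation between the two visits. The units agree only at ρ = 0.5, where √(2 × 0.5) = 1. The protocol gives no ρ. If one absolute shift, set at 0.25 to 0.5 SD of the paired difference, acts on both contrasts, the Mann-Whitney rejection rate is:
- ρ = 0.8 (factor 0.632, shift 0.158 to 0.316 SD): 6% to 11%
- ρ = 0.5 (factor 1, shift 0.25 to 0.5 SD): 8% to 21%
- ρ = 0.2 (factor 1.265, shift 0.316 to 0.632 SD): 11% to 32%

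**Step 4: effect on estimation.** A shift of b SD enters the estimated standardised difference one for one. With no true difference, an assumed shift of 0.25 to 0.5 SD would on average appear as an effect of 0.25 to 0.5 SD. For a pilot whose product is an effect size, this matters more than the false-positive rate.

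**The case against.** The strongest reply is that the sentence may mean less than it seems to. In a non-randomised study in which every participant receives ULM, followed at once by a remark about patients, it may say only that taking part and being examined cannot be concealed. It does not forbid coded reading, and reading order could be set out in an imaging manual that is not shown. That is a fair reading of the intention. The wording remains unqualified, however, and no section provides what the narrower reading would leave room for.

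A second reply is that the protocol never describes the outcomes as dependent on the operator or reader. It does not mention selection of clips, placement of regions of interest or curve fitting, and it does not say which steps are manual. This stands. If extraction is fully automatic, the risk shrinks. Segmentation, the step most suggestive of judgement, appears only as an example under the secondary objectives, not in the list of primary outcomes. The one operator choice that the protocol states is which kidney to scan, and masked reading would not touch it.

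A third reply is that the study is exploratory, so false-positive rates are a poor measure of harm. This also stands, and biased effect sizes are the better description.

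A reader might infer more than the document supports:
- That the two contrasts are the study's whole result. They are not: the primary objective is also descriptive, and the secondary objectives are correlations.
- That the percentages above measure bias in this trial. They follow from an assumed shift that nothing in the protocol anchors.
- That kidney size could give away the cohort but never the visit. The protocol offers no basis for this, and both cohorts share the age range of 3 to under 18 years.

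**Conclusion.** The point holds in a limited form. The statement that blinding is impossible is correct for the scanning operator and too broad for image processing and reading, which the protocol's own workflow allows on coded files. As written, the plan permits an avoidable bias in an unrandomised study with a directional hypothesis. What could be affected is the before/after and early/late contrasts, the correlations with laboratory values, and the effect sizes handed on to later studies.

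This rests on one assumption, that some part of visualisation, segmentation or quantification involves judgement. The protocol neither confirms nor excludes it. The size of the bias cannot be derived from the document, and the figures above show only how sensitive comparisons of this size are to an assumed shift. It does not follow that the readings will be biased, or that the primary outcomes are established to depend on the reader. The change should be made before reading starts, because images already read with cohort and visit known cannot afterwards be treated as masked by the same reader.

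**What to change.** Replace the first sentence of the Blinding section with wording to this effect: The scanning operator and the patients cannot be blinded. ULM post-processing, segmentation and perfusion quantification are done on coded files in random order, with cohort, visit, date and laboratory results hidden. The two examinations of one patient are not presented together.

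It would help to add one sentence saying which steps are automatic and which need a reader's decision, so that the remaining risk can be judged.

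The cost is one protocol paragraph and reading in batches. The 30 patients and 40 examinations do not change, no procedure is added for the children, and no extra reader is strictly needed. There are limits, which the protocol should state. Masking may be incomplete, because image features can hint at the cohort or visit and a person who both scanned and reads may recognise some of only 40 examinations. Bias from unmasked scanning and from the choice of kidney remains.

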### Graphical design of study flow

**Figure 1: Course of Study**

**STUDY POPULATION / IN- AND EXCLUSION CRITERIA**

Early therapeutic effects	Late therapeutic effects
Planned number of patients	
N = 10 ALL (recently diagnosed ALL)	N = 20 ALL (completed oncological treatment)
Planned number of examinations for each participant	
2 (before first CPM according to therapy protocol and after completion of intensive therapy)	1
Inclusion criteria	

 
- Diagnosed acute lymphatic leukemia
 
- Treatment day < 50 according to therapy protocol / no administration of CPM before first examination
 
- From 3 years to < 18 years
 
	
 
- Diagnosed acute lymphatic leukemia
 
- Completed oncological treatment
 
- From 3 years to < 18 years
 

Exclusion criteria	

 
- Known allergic disposition to SonoVue / other contrast agents
 
- Tattoo in the area of the examination field
 
- Pregnancy
 
- Breastfeeding mothers
 
- Contraindication for the use of Sonovue
 
- Critical condition
 
	
 
- Known clinically evident renal impairment
 
- Known allergic disposition to SonoVue / other contrast agents
 
- Tattoo in the area of the examination field
 
- Pregnancy
 
- Breastfeeding mothers
 
- Contraindication for the use of Sonovue
 
- Critical condition
 

**Number of patients**

As this is a pilot study, it is not possible to calculate the exact number of patients. It is planned to include 30 patients (in total 40 examinations). The planned sample size of 30 participants (10 during therapy and 20 in follow-up) was determined based on the annual incidence of ALL at our center, which is approximately 15 cases per year. Recruitment within the intended timeframe of 12–18 months is therefore considered feasible. In addition, the study has a pilot character, aiming to provide the first data set for estimating effect sizes and to serve as a foundation for the design of larger subsequent studies. 10 patients who will undergo an ULM examination of the kidney before the start of chemotherapy, latest before therapy day 50 before the first application of high-dose methotrexate or cyclophosphamide (Timepoint 1). After completion of intensive therapy (after administration of cyclophosphamide and high-dose methotrexate), they will receive a follow-up ULM

Contents are confidential. No disclosure to third parties.

examination (Timepoint 2) approx. 6-9 months after the first ULM examination. In addition, 20 different patients who have completed treatment for ALL and are seen during aftercare will be included in the study.

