**Total duration of the study**

The expected total duration of the study is 18 months.

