## **RISK-BENEFIT-ANALYSIS**

### **Study-related risks with ULM**

#### ***Insertion of a peripheral venous catheter (pVK)***

For the examination using ULM in the 20 individuals who have completed treatment for ALL and are seen during aftercare it is necessary to insert a peripheral venous catheter (pVK) (e.g. in the hand, crook of the elbow). The insertion of a peripheral venous catheter is generally feasible without limitations even in children after completion of chemotherapy. For this study, catheter placement will be combined with routine blood sampling to avoid additional burden. As with any blood sampling, this can result in injury to the skin at the entry point. There is also a risk of infection at the entry site, but this is very low given the short time of insertion of approx. 2 hours.

In the 10 individuals who will be assessed before therapy day 50 (Visit 1) and after completion of intensive chemotherapy (Visit 2), the routinely implanted central venous catheter will be used for the administration of the contrast agent. In these cases, no additional pVK is required. Laboratory chemistry parameters (including BB, Diff, Glucose, Na, K, Cl, Ca, LDH, Crea, Cystatin C, Uric Acid, CRP, Albumin, Ferritin, Total Protein) and urinalysis including urinary status, proteinuria/haematuria as well as conventional ultrasound assessment are routinely performed during therapy and aftercare. So, in addition to ULM, no extra procedure will be undertaken in the frame of this study.

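### Can an expected total of 18 months hold 12–18 months of recruitment and a second scan 6–9 months after the first?

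*Protocol*

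**What the plan says.** Three statements about time have to be read together.

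- **Recruitment** (Protocol, Number of patients): "Recruitment within the intended timeframe of 12–18 months is therefore considered feasible". The window is given once, for all 30 participants, and is supported by the centre's ALL incidence, "which is approximately 15 cases per year".
- **Second scan** (same section): for the 10 newly diagnosed patients, "approx. 6-9 months after the first ULM examination".
- **Total duration** (Total duration of the study): "The expected total duration of the study is 18 months".

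The second scan is plainly part of the study. The section on study arms says "Patients with recently diagnosed ALL will receive ULM at two timepoints". The section on the peripheral venous catheter describes this group as "assessed before therapy day 50 (Visit 1) and after completion of intensive chemotherapy (Visit 2"). The workload is stated as "It is planned to include 30 patients (in total 40 examinations"), a count that includes the second scans.

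The limits on the first scan follow each patient's treatment, not the study calendar: treatment day below 50 and "no administration of CPM before first examination". The readable text gives no last calendar date for a first scan. The course-of-study figure could not be read for this review, so that statement covers the text only.

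**The concern.** Read at the top of its range, recruitment alone uses the whole 18 months, and a patient enrolled near the end still has a scan due 6–9 months later. The stated total then looks too short by up to 9 months, and nothing in the text says that the paired cohort is to be filled first.

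The 10 pairs are the only within-patient data on change over treatment, and the pilot is meant to supply effect sizes for later studies. If the study closed at month 18 with second scans outstanding, some of a very small set of pairs would be lost.

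**Working it through.** **Inputs.** From Number of patients: 10 paired and 20 single-visit patients, recruitment 12–18 months, interval 6–9 months, about 15 new cases a year. From Total duration of the study: 18 months.

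**1. Examination count.** 10 × 2 + 20 × 1 = 40. This reproduces the stated figure and confirms that the second scans are counted.

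**2. Total if paired enrolment runs to the end of the window** (recruitment + interval):

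| Recruitment | Interval 6 months | Interval 9 months |
|---|---|---|
| 12 months | 18 | 21 |
| 18 months | 24 | 27 |

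One of the four corners gives the stated 18.

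**3. Latest first scan compatible with 18 months** (18 − interval): 18 − 6 = month 12; 18 − 9 = month 9.

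**4. Accrual at the Protocol's own rate.** 15/12 = 1.25 cases a month. At full uptake, 10/1.25 = 8 months. The last second scan then falls at 8 + 6 = 14 to 8 + 9 = 17 months, inside 18.

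**5. Uptake needed to finish by month 18.**
- By month 12, 15 cases are expected: 10/15 = 67%.
- By month 9, 15 × 9/12 = 11.25 cases are expected: 10/11.25 = 89%.
- If patients already under treatment day 50 at opening are counted, at most 15 × 50/365 = 2.05 of them under steady incidence, the shares fall to 10/17.05 = 59% and 10/13.30 = 75%.

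**6. End date at lower uptake** (assumed values; the Protocol gives none). Months to 10 pairs = 10/(1.25 × uptake).

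| Uptake | Months to 10 pairs | Last second scan (month) |
|---|---|---|
| 100% | 8.0 | 14.0–17.0 |
| 80% | 10.0 | 16.0–19.0 |
| 60% | 13.3 | 19.3–22.3 |
| 50% | 16.0 | 22.0–25.0 |

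These are expected values. With Poisson arrivals, the chance of 10 pairs by month 12 is 93% at full uptake and 76% at 80% uptake; by month 9 it is 69% and 41%.

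**7. Scans falling after month 18.** With even enrolment over the window, the number is 10 × max(0, window − (18 − interval))/window:
- 12 and 6 months: 0
- 12 and 9 months: 10 × 3/12 = 2.5
- 18 and 6 months: 10 × 6/18 = 3.3
- 18 and 9 months: 10 × 9/18 = 5

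These scans are late, not lost. Losing them requires a closure at month 18. The duration is described as expected, and the only rule for stopping the whole study (Withdrawal criteria) concerns increased risk to participants, not the calendar.

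**The case for a change.** The strongest case for a change is that recruitment window, visit interval and study duration are protocol items, all three are given, and they do not fit across most of their ranges. The recruitment sentence follows a description of both cohorts, so it cannot be confined to the single-visit patients. Full uptake is unlikely: exclusions and consent reduce the 15 cases a year, and so does the lower age limit of 3 years unless the 15 already reflects it, which the Protocol does not say. Words such as approximate and expected cover a few weeks, not 3 to 9 months. One sentence would settle the matter.

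Much of this stands. The text does not explain how the three figures fit together, and a finish after month 18 is a realistic prospect: at 60% uptake it is what one would expect. What does not stand is the step from there to harm. The second scan is timed from each patient's own first scan and treatment, so a later study end leaves the interval, the number of pairs and the comparison unchanged. The 2.5 to 5 late scans become losses only if even enrolment over the whole window is combined with a closing date that the text does not set. A one-line clarification would be tidy, but it would only write down a calendar decision that a single-centre team of this size makes as accrual unfolds.

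**Conclusion.** The concern does not call for a change. The stated ranges give 18 to 27 months if paired enrolment uses the whole window, against 18 expected. That is a loose fit at the upper end, not a miscalculated figure. The 18 months is attainable on the Protocol's own incidence: 10 pairs in 8 months and a finish by month 14–17, provided every new case is eligible and agrees. Between 67% and 89% of new cases must be enrolled for the last pair to be complete by month 18.

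Below that uptake, the consequence of following the plan as written is a later end date, for example month 19.3–22.3 at an assumed 60%. The 10 pairs, the 40 examinations and the analysis stay as they are. This rests on two readings: that 18 months is an expectation and not a hard stop, as its wording indicates, and that the single-visit patients, who need one examination each, can fill the later months. A fixed administrative closure at month 18 would change the assessment, but the readable text contains none.
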